16.7 MISSING CAUSAL RELATIONSHIP TO INVESTIGATIONAL PRODUCT FOR ADVERSE EVENTS

If the causal relationship to the investigational product is missing for an AE that started on or after the date of the first dose of double-blind investigational product, a causality of yes will be assigned. The imputed values for causal relationship to double-blind treatment will be used for the incidence summary; the values will be shown as missing in the data listings.

16.8 MISSING DATE INFORMATION FOR ADVERSE EVENTS

The following imputation rules only apply to cases in which the start date for AEs is incomplete (i.e., partly missing).

Missing month and day

- If the year of the incomplete start date is the same as the year of the first dose of double-blind investigational product, the month and day of the first dose of double-blind investigational product will be assigned to the missing fields
- If the year of the incomplete start date is before the year of the first dose of double-blind investigational product, *December 31* will be assigned to the missing fields
- If the year of the incomplete start date is after the year of the first dose of double-blind investigational product, *January 1* will be assigned to the missing fields

Missing month only

- If only the month is missing, the day will be treated as missing and both the month and the day will be replaced according to the above procedure

Missing day only

- If the month and year of the incomplete start date are the same as the month and year of the first dose of double-blind investigational product, the day of the first dose of double-blind investigational product will be assigned to the missing day
- If either the year of the incomplete start date is before the year of the date of the first dose of double-blind investigational product or if both years are the same but the month of the incomplete start date is before the month of the date of the first dose of double-blind investigational product, the last day of the month will be assigned to the missing day
- If either the year of the incomplete start date is after the year of the date of the first dose of double-blind investigational product or if both years are the same but the month of the incomplete start date is after the month of the date of the first dose of double-blind investigational product, the first day of the month will be assigned to the missing day

If the stop date is complete and the imputed start date as above is after the stop date, the start date will be imputed by the stop date.

If the start date is completely missing and the stop date is complete, the following algorithm will be used to impute the start date:

- If the stop date is after the date of the first dose of double-blind investigational product, the date of the first dose of double-blind investigational product will be assigned to the missing start date
- If the stop date is before the date of the first dose of double-blind investigational product, the stop date will be assigned to the missing start date

16.9 MISSING DATE INFORMATION FOR PRIOR OR CONCOMITANT MEDICATIONS

For prior or concomitant medications, including rescue medications, incomplete (i.e., partly missing) start dates and/or stop dates will be imputed. When the start date and the stop date are both incomplete for a patient, the start date will be imputed first.

16.9.1 Incomplete Start Date

The following rules will be applied to impute the missing numeric fields for an incomplete prior or concomitant medication start date. If the stop date is complete (or imputed) and the imputed start date is after the stop date, the start date will be imputed using the stop date.

Missing month and day

- If the year of the incomplete start date is the same as the year of the first dose of double-blind investigational product, the month and day of the first dose of double-blind investigational product will be assigned to the missing fields
- If the year of the incomplete start date is before the year of the first dose of double-blind investigational product, *December 31* will be assigned to the missing fields
- If the year of the incomplete start date is after the year of the first dose of double-blind investigational product, *January 1* will be assigned to the missing fields

Missing month only

- If only the month is missing, the day will be treated as missing and both the month and the day will be replaced according to the above procedure

Missing day only

- If the month and year of the incomplete start date are the same as the month and year of the first dose of double-blind investigational product, the day of the first dose of double-blind investigational product will be assigned to the missing day
- If either the year of the incomplete start date is before the year of the date of the first dose of double-blind investigational product or if both years are the same but the month of the incomplete start date is before the month of the date of the first dose of double-blind investigational product, the last day of the month will be assigned to the missing day
- If either the year of the incomplete start date is after the year of the date of the first dose of double-blind investigational product or if both years are the same but the month of the incomplete start date is after the month of the date of the first dose of double-blind investigational product, the first day of the month will be assigned to the missing day

16.9.2 Incomplete Stop Date

The following rules will be applied to impute the missing numeric fields for an incomplete prior or concomitant medication stop date. If the date of the last dose of double-blind investigational product is missing, replace it with the last visit date in the imputations described below. If the imputed stop date is before the start date (imputed or non-imputed start date), the imputed stop date will be equal to the start date.

Missing month and day

- If the year of the incomplete stop date is the same as the year of the last dose of double-blind investigational product, the month and day of the last dose of double-blind investigational product in the study will be assigned to the missing fields
- If the year of the incomplete stop date is before the year of the last dose of double-blind investigational product, *December 31* will be assigned to the missing fields
- If the year of the incomplete stop date is after the year of the last dose of double-blind investigational product, *January 1* will be assigned to the missing fields

[figure not shown]
Missing month only

- If only the month is missing, the day will be treated as missing and both the month and the day will be replaced according to the above procedure

Missing day only

- If the month and year of the incomplete stop date are the same as the month and year of the last dose of double-blind investigational product, the day of the last dose of double-blind investigational product will be assigned to the missing day
- If either the year of the incomplete stop date is before the year of the date of the last dose of double-blind investigational product or if both years are the same but the month of the incomplete stop date is before the month of the date of the last dose of double-blind investigational product, the last day of the month will be assigned to the missing day
- If either the year of the incomplete stop date is after the year of the date of the last dose of double-blind investigational product or if both years are the same but the month of the incomplete stop date is after the month of the date of the last dose of double-blind investigational product, the first day of the month will be assigned to the missing day

17.0

CHANGES TO ANALYSES SPECIFIED IN PROTOCOL

The major change to the analyses specified in the Protocol Amendment #3, dated 25 March 2019, is as follows:

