Medical and surgical history/physical findings will be classified by system organ class and preferred term using the *Medical Dictionary for Regulatory Activities*, version 16.1 or newer. The number and percentage of patients with abnormalities in medical and surgical histories in each system organ class and preferred term will be summarized by treatment group for the Safety Population. Psychiatric history of MDD and nondrug psychiatric treatment history will also be summarized by treatment group for the Safety Population.

The *World Health Organization Drug Dictionary*, version March 2013 or newer, will be used to classify prior and concomitant medications by therapeutic class and drug name.

Prior medication is defined as any recorded medication taken before the date of the first dose of double-blind investigational product. *Concomitant medication* is defined as any medication taken on or after the date of the first dose of double-blind investigational product.

Both prior and concomitant medications use will be coded by drug name and therapeutic class. The use of prior and concomitant medications will be summarized by the number and percentage of patients receiving each drug within each therapeutic class in each treatment group for the Safety Population. If a patient took a specific medication multiple times or took multiple medications within a specific therapeutic class, that patient would be counted only once for the coded drug name or therapeutic class.

Summaries for concomitant medication use will be presented for the double-blind treatment period and the double-blind down-taper period, separately. Any concomitant medications started after the date of the last dose of double-blind investigational product in the study will not be presented in the summary tables but will be included in the patient data listings.

9.0

EXTENT OF EXPOSURE AND TREATMENT COMPLIANCE

9.1

EXTENT OF EXPOSURE

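### For one pattern of partial dates, SAP 16.9 tabulates a drug recorded as stopped before treatment as concomitant and not prior, and rules 16.9.1 and 16.9.2 conflict

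*SAP*

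**What the plan says.** SAP 16.9 sets the order: "When the start date and the stop date are both incomplete for a patient, the start date will be imputed first".

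SAP 16.9.1 imputes the start against the first dose. If month and day are missing and the year is the first-dose year, "the month and day of the first dose of double-blind investigational product will be assigned to the missing fields". A start that lacks only its month goes the same way: "If only the month is missing, the day will be treated as missing and both the month and the day will be replaced" under that rule. The section also has a consistency rule: "If the stop date is complete (or imputed) and the imputed start date is after the stop date, the start date will be imputed" from the stop date.

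SAP 16.9.2 imputes the stop against the last dose. If only the day is missing and the recorded month is before the last-dose month, "the last day of the month will be assigned to the missing day". Its own consistency rule runs the other way and moves an earlier stop to the start; it opens with "If the imputed stop date is before the start date (imputed or non-imputed start date), the imputed stop date will be equal to".

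SAP 8.0 then classifies the record. "Prior medication is defined as any recorded medication taken before the date of the first dose of double-blind investigational product", and a concomitant medication "is defined as any medication taken on or after the date of the first dose of double-blind investigational product". Both are counted by treatment group in the Safety Population.

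**The concern.** The two consistency rules point in opposite directions when both dates are partial. Section 16.9.1 pulls the start back to the stop, and 16.9.2 pushes the stop forward to the start. In the order that 16.9 prescribes, no imputed stop exists when 16.9.1 runs, and 16.9.2 later makes the two dates equal. So 16.9.2 decides, and the mention of an imputed stop in 16.9.1 has no effect on these records. A programmer who gives effect to those words would classify the same record the other way.

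Where the stop month is recorded and lies before the first-dose month, the prescribed order replaces recorded information with an invented date. Each such record adds a false entry to the concomitant table and removes a true one from the prior table. Protocol 9.4.8 collects 5 years of psychotropic history and 12 months of other medication, so recalled, partial dates are plausible.

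**Working it through.** The plan gives no figure to reproduce, so the check applies the rules as written. The dates are illustrative assumptions: first dose 10 June 2017 and last dose 11 August 2017, which is first dose + 62 days (8 weeks of treatment plus the 1-week taper, 63 dosing days).

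**The failing record.** Start 2017 (year only), stop March 2017 (day missing).

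1. 16.9 takes the start first. The year equals the first-dose year, so 16.9.1 gives start = 10 June 2017.
2. 16.9.2 imputes the stop to the end of the recorded month: 31 March 2017.
3. 31 March is before 10 June, so 16.9.2 sets stop = 10 June 2017.
4. Under 8.0 the start is not before first dose, so the drug is not prior. The stop is on first dose, so it is concomitant.

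If the 16.9.1 consistency rule is applied at step 3 instead, start = stop = 31 March 2017, which is prior and not concomitant. The latest stop that the record allows is 30 + 31 + 10 = 71 days before first dose.

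**Neighbouring patterns under the rules as written, same dosing dates.**

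| Start recorded | Stop recorded | Imputed start | Imputed stop | Class |
|---|---|---|---|---|
| 2017 | Mar 2017 | 10 Jun 2017 | 10 Jun 2017 | concomitant only (wrong) |
| 2017 | 20 Mar 2017 | 20 Mar 2017 | complete | prior (right) |
| Feb 2017 | Mar 2017 | 28 Feb 2017 | 31 Mar 2017 | prior (right) |
| 2016 | Mar 2017 | 31 Dec 2016 | 31 Mar 2017 | prior (right) |
| 2016 | Mar 2016 | 31 Dec 2016 | 31 Dec 2016 | prior (right class, stop date moved) |

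The failure therefore needs three things together: start month missing, start year equal to the first-dose year, and stop recorded to an earlier month of that year with the day missing.

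**Scope.** Within that pattern, every first-dose date in 2017 was paired with every earlier month of the year as the stop month, and all 2017 of 2017 pairs were misclassified. A wider grid took drugs stopped 1 to 365 days before first dose, with each date complete, lacking the day, or lacking month and day. Only records whose stop, as recorded, still shows a stop before first dose were kept. Failures occurred only where the start lacked month and day and the stop lacked its day:

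- first dose 20 January 2018: 0 of 2900
- first dose 15 June 2018: 253 of 2958
- first dose 20 November 2018: 990 of 2900

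Letting 16.9.1 govern brings all three to 0. These counts show which records can fail. They are not expected frequencies.

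**Test of two remedies.**

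- *Stop imputed first in every case, with any incomplete start capped at it.* This clears the 2017 failures but breaks another pattern. Take start September 2017 and stop 2017 (year only). The current rules give start = stop = 1 September 2017, after last dose, so the drug goes to the listings only, as 8.0 intends. Stop-first gives stop = 11 August 2017 and caps the start there, so a drug begun after treatment is tabulated as concomitant. This happened in 1350 of 1350 pairs of first-dose date and later start month, with last dose in 2017.
- *Start capped at the stop only when the start month is missing and the stop month is recorded.* Failures were 0 of 2017 and mirror errors 0 of 1350.

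**The case against.** The strongest defence is that counting a drug as concomitant when in doubt is a customary, cautious convention, that the affected tables are descriptive with no test attached, and that the pattern is narrow. The last two points stand and set the severity. The first does not, because here there is no doubt about overlap. A stop in March excludes use in June as surely as a stop on 20 March does, and the SAP already classifies the latter as prior.

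A reader might infer more than the documents support:

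- *That washed-out drugs in general become concomitant, or that the 5-year history makes this common.* Starts in earlier calendar years stay prior. The 2017 of 2017 count covers only the failing pattern and says nothing about how many records have it.
- *That false prohibited-medication deviations or failed washouts follow.* Neither document says that deviations are derived from imputed dates, and Protocol 9.7.2 has important deviations reviewed before database lock and unblinding. Exclusion 6 is an eligibility criterion applied at Visits 1 and 2, before any SAP imputation, and its 2-week period concerns stabilisation on an allowed alternative. In the last row of the table the stop date moves but the class does not.
- *That the adverse-event rules in SAP 16.8 avoid the problem.* They cap an imputed start only at a complete stop date, so an event with the same two partial dates would also start on the first-dose date.

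**Conclusion.** The point holds in a narrow form and is minor. Followed in their stated order, the SAP 16.9 rules give a classification that contradicts the record in one pattern of partial dates, and 16.9.1 and 16.9.2 give opposite answers for that record. The effect is confined to the prior and concomitant medication summaries. The CDRS-R and CGI-S analyses, the sample size and the type I error control do not depend on it. The mechanism follows from the text alone. The example dates are assumptions, and the documents do not allow an estimate of how many records or patients are involved.

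**What to change.** Add one sentence to SAP 16.9: when both dates are partial and the imputed stop precedes the imputed start, the 16.9.1 rule governs (start set to the imputed stop) if the start month is missing and the stop month is recorded; otherwise the 16.9.2 rule stands. Cross-refer to it from both consistency sentences so that only one reading is possible.

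Do not change the order to stop-first for all records, because of the mirror error shown above.

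The cost is one sentence and a small condition in the date-derivation program. No data collection or efficacy output changes.

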APPENDIX I PATTERN-MIXTURE MODEL DETAILS

For repeated measures with the monotone missing mechanism, the pattern-mixture model with non-future dependent missing assumption, proposed by Kenward et al. (2003), provides a feasible solution to accommodate certain missing not at random (MNAR) mechanism. The methodology relies on constructing unidentifiable conditional densities using identifiable densities and borrows techniques from standard multiple imputation.

1. Non-Future Dependent Missing Assumption

Assume there are T designed visits in a longitudinal study and let y_i ($i = 1, 2, \dots, T$) represent patient's measurement at Visit i . When the missing mechanism is monotone, the pattern of missing data can be defined by the number of measurements (L) actually observed from the patient. Let $f(y_i, \dots, y_j | L = t)$ denote the conditional density of y_i, \dots, y_j , given that the last observed measurement is at Visit t . Then the overall density function for Pattern t can be written as

$$f(y_1, \dots, y_T | L = t) = f(y_1, \dots, y_t | L = t) f(y_{t+1} | y_1, \dots, y_t, L = t) \times \prod_{s=t+2}^T f(y_s | y_1, \dots, y_{s-1}, L = t) \quad (1)$$

Note on the right hand side of (1) the first factor is clearly identifiable from the observed data, while the second and the beyond are not, due to lack of available data. The second factor $f(y_{t+1} | y_1, \dots, y_t, L = t)$ could be identifiable based on an assumed relationship between $f(y_{t+1} | y_1, \dots, y_t, L = t)$ and $f(y_{t+1} | y_1, \dots, y_t, L \geq t + 1)$. The third and beyond factors $f(y_s | y_1, \dots, y_{s-1}, L = t)$ (with all $s \geq t + 2$) could be identifiable with the help of non-future dependent missing assumption.

For longitudinal data with dropouts, non-future dependent (NFD) missing mechanism (Kenward et al., 2003) assumes that the unidentifiable conditional distributions of y_s ($s \geq t + 2$), given earlier measurements, in Pattern t , is equal to the corresponding distribution in patterns $L \geq s - 1$:

$$f(y_s | y_1, \dots, y_{s-1}, L = t) = f(y_s | y_1, \dots, y_{s-1}, L \geq s - 1) \quad (2)$$

The right hand side of (2) can further be partitioned into

$$f(y_s | y_1, \dots, y_{s-1}, L \geq s-1) = \sum_{j=s-1}^T \omega_{s-1,j} \cdot f(y_s | y_1, \dots, y_{s-1}, L = j) \quad (3)$$

Where mixture probabilities $\omega_{s-1,j}$ are:

$$\omega_{s-1,j} = \frac{\alpha_j f(y_1, \dots, y_{s-1} | L = j)}{\sum_{t=s-1}^T \alpha_t f(y_1, \dots, y_{s-1} | L = t)}, \text{ and } \alpha_j \text{ represents the fraction of} \quad (4)$$

patients from Pattern j .

Each factor of the unidentifiable conditional distribution of y_s ($s \geq t + 2$) on the right side of (1) can be expressed using the following:

- $f(y_s | y_1, \dots, y_{s-1}, L = s-1)$, the unidentifiable conditional distribution of the first missing in pattern $s-1$,
- $f(y_s | y_1, \dots, y_{s-1}, L = j)$, the identifiable conditional distributions of y_s given y_1, \dots, y_{s-1} of pattern j ($j \geq s$), and
- α_j , the fraction of patients from pattern j ($j \geq s-1$).

So under NFD, all the unidentifiable conditional distribution on the right side of (1) can be estimated and missing value could be therefore imputed based on the assumption for unidentifiable conditional distribution of the first missing.

We re-formulate the partition in (3), for $s \geq t + 2$, as the following:

$$f(y_s | y_1, \dots, y_{s-1}, L = t) = \delta_{s-1} f(y_s | y_1, \dots, y_{s-1}, L = s-1) + (1 - \delta_{s-1}) f(y_s | y_1, \dots, y_{s-1}, L \geq s) \quad (5)$$

for $s \geq t + 2$ with $\delta_{s-1} = \omega_{s-1,s-1}$.

Therefore, under monotone missing and NFD assumption, the unidentifiable conditional densities for Visit s in Pattern t ($s \geq t + 2$) can be expressed as a mixture distribution of $f(y_s | y_1, \dots, y_{s-1}, L = s - 1)$ - the unidentifiable conditional distribution of the first missing measurement y_s in Pattern $s - 1$, and $f(y_s | y_1, \dots, y_{s-1}, L \geq s)$ - the identifiable conditional distribution of y_s from all the patterns with observed data at Visit s or beyond:

$$f(y_s | y_1, \dots, y_{s-1}, L \geq s) = \sum_{j=s}^T \lambda_{s-1,j} f(y_s | y_1, \dots, y_{s-1}, L = j) \quad (6)$$

where the mixture probability

$$\lambda_{s-1,j} = \omega_{s-1,j} / (1 - \omega_{s-1,s-1}) = \frac{\alpha_j f(y_1, \dots, y_{s-1} | L = j)}{\sum_{t=s}^T \alpha_t f(y_1, \dots, y_{s-1} | L = t)} \text{ for } j \geq s, \text{ where } \alpha_j \text{ is the fraction of} \quad (7)$$

patients from Pattern j .

The conditional densities for the first missing are selected as:

$$f(y_s | y_1, \dots, y_{s-1}, L = s - 1) = f(y_s - \Delta | y_1, \dots, y_{s-1}, L \geq s) \text{ for } s = 2, \dots, T, \quad (8)$$

Note that the two distributions only differ by a shift (Δ) parameter. When $\Delta = 0$, the missing value y_s in Pattern $s - 1$ is imputed based on the distribution of all observed data up to Visit s , as a result, leading to missing at random (MAR) missingness. When $\Delta \neq 0$, (8) will introduce a scenario of MNAR. The similar idea was also presented in the recent publication “The Prevention and Treatment of Missing Data in Clinical Trials” by the National Academies Press. The selection of the plausible values for the shift parameter (Δ) is discussed in Section 3.

Note that per recommendation in Wang and Daniels (2011), only the observed data within pattern is assumed to be multivariate normal. The observed data distribution can be expressed in terms of the marginal distribution of baseline measurement and the conditional distributions of postbaseline measurements given earlier measurements. Assuming that these distributions are normal, the linear regression of each observation on prior observations will yield least-squares estimates of model parameters that can be utilized for independent posterior draws of model parameters for observed data. Multiple imputation approach will be used to estimate the overall mean at the final time point.

2. Imputation Procedure

All the missing data will be imputed to create complete datasets, then statistical analysis can be performed using appropriate techniques such as ANCOVA. The imputation can accommodate MNAR missing data mechanisms, based on the theory discussed in the previous section.

The model parameters for each dropout pattern, i.e., the mean, variance and proportions of observations in each pattern, are drawn from their posterior distributions prior to the imputation of missing data for a single imputation.

The details of imputation within a pattern, say Pattern t , are as the following:

Step 1. Impute the first missing value y_{t+1} for each patient in Pattern t ($t = 1, \dots, T - 1$):

- a. Compute estimates of mixture probabilities $\lambda_{s-1,j}$ in (7) with $s = t+1$ given the posterior draw of proportions of observations in each pattern and the posterior draw of regression parameters for the observed data.
- b. Draw a random integer from $\{s, \dots, T\}$ to index a component distribution on the right hand side of (6), using mixture probabilities obtained in a). Draw y_{t+1}^* from the identified component normal distribution. Impute the missing y_{t+1} as $\tilde{y}_{t+1} = y_{t+1}^* + \Delta$.

Step 2. Impute the rest of the missing values of $y_{t+2}, y_{t+3}, \dots, y_T$ for patients in Pattern t :

Starting with imputation for y_{t+2} , first, similar to Step 1, draw y_{t+2}^* from the normal mixture (6) based on the observed y_1, \dots, y_t and the already imputed \tilde{y}_{t+1} for the patient.

Then the missing y_{t+2} is imputed as $\tilde{y}_{t+2} = y_{t+2}^* + \Delta$ with probability δ_{t+1} and as $\tilde{y}_{t+2} = y_{t+2}^*$ with probability $1 - \delta_{t+1}$, where the mixture probability $\delta_{t+1} = \omega_{t+1,t+1}$ is obtained from (4) given the posterior draw of proportions of observations in each pattern and the posterior draw of regression parameters for the observed data.

Missing values of y_{t+3} through y_T can be imputed similarly as y_{t+2} .

To summarize, the imputations of y_{t+1} through y_T is done recursively within each Pattern t (for all $t = 1, \dots, T - 1$) to create a complete dataset after imputation is done for all patterns with missing values.

The above imputation procedure is applied to all subjects in each missing data pattern to create a single imputed data set. Repeating the process of drawing parameters from the posterior distribution and imputing missing data given the posterior draw m times will yield m imputed data sets. The observed or imputed values at the final data point are averaged to obtain the overall mean estimate for each imputed data set, and the multiple imputation estimate is obtained by averaging the estimates across m imputations.

[figure not shown]
In this sensitivity analysis, m is set to equal to 20. The value of m is discussed in the context of imputation efficiency in standard multiple imputation theory (Rubin, 1987, p. 114), and $m = 20$ would provide at least 96% of relative efficiency as compared with using an large number of imputations (SAS/STAT User's Guide, p. 3796).

3. Determination of the Shift Parameter Values

